## Division & Personnel

### Division

What Division/Department does the PI belong to?

Division on Substance Use Disorders

Within the division/department, what Center or group are you affiliated with, if any?

STARS

### Unaffiliated Personnel

List investigators, if any, who will be participating in this protocol but are not affiliated with New York State Psychiatric Institute or Columbia University. Provide: Full Name, Degrees and Affiliation.

none

## Procedures

**To create the protocol summary form, first indicate if this research will include any of the following procedures**

- Psychiatric Assessment
- Collection of Biological Specimens
- Medication Trial
- Use of Investigational Drug or Device
- Off-label Use of Drug or Device

## Population

**Indicate which of the following populations will be included in this research**

- Medically and Psychiatrically Healthy Subjects
- Adults
- Adults over 50
- Substance Users

## Research Support/Funding

Will an existing internal account be used to support the project?

No

Is the project externally funded or is external funding planned?

Yes

Select the number of external sources of funding that will be applicable to this study

## Funding Source #1

Is the PI of the grant/contract the same as the PI of the IRB protocol?

Yes

Select one of the following

The grant/contract is currently funded

Source of Funding

Foundation

Sponsor

Smithers Foundation

Select one of the following

Single Site

Business Office

RFMH

Does the grant/contract involve a subcontract?

No

## Study Location

Indicate if the research is/will be conducted at any of the following

Other Columbia University Medical Center Facilities

This protocol describes research conducted by the PI at other facilities/locations

No

## Lay Summary of Proposed Research

### Lay Summary of Proposed Research

The proposed protocol is an open label outpatient pilot trial of the feasibility and tolerability of pregabalin (Lyrica) in the treatment of alcohol use disorder. Pregabalin is commonly used for the treatment of pain issues such as fibromyalgia (chronic pain in your body), diabetic nerve pain, spinal cord injury nerve, and pain after shingles. We plan to enroll 20 participants in a 9-week trial. The ideal dosing, tolerability, and safety of pregabalin will be tested in outpatients with Alcohol Use Disorder (AUD). The primary objective of the study is to determine the feasibility and tolerability of pregabalin in promoting alcohol abstinence among individuals with an alcohol use disorder.

## Background, Significance and Rationale

### Background, Significance and Rationale

Alcohol Use Disorder (AUD) is a common substance use disorder (Regier et al. 1990, Kessler et al. 1994, Grant and Harford 1995, Grant et al. 2004, Kessler et al. 2005, Kessler et al. 2005) responsible for substantial morbidity, mortality (McGinnis and Foege 1999, Mokdad et al. 2004), and economic costs in the U.S. (Harwood 2000). A notably absent option among the available pharmacotherapies for alcohol dependence is a medication that can be administered to actively drinking outpatients that protects against withdrawal and promotes abstinence.

The neuroexcitatory state associated with alcohol withdrawal and the post-acute withdrawal period of neuroadaptation (also known as “protracted withdrawal”) is characterized by insomnia, anxiety, and alcohol craving (Myrick et al. 2001). Emergence of these symptoms, which can be relieved by alcohol consumption, may be associated with relapse drinking in newly abstinent individuals. Because a reduction or cessation of alcohol consumption by an alcohol-dependent individual results in neuroexcitation, neuroinhibitory agents, such as pregabalin, are logical potential therapeutic strategies.

Most pharmacotherapy clinical trials for alcohol use disorders can be considered relapse prevention trials, as they have been conducted in abstinent, recently detoxified patients, and the evidence suggests that the efficacy of two of the FDA-approved medications for AUD (naltrexone and acamprosate) may depend on baseline abstinence (Garbutt et al. 2005, Anton et al. 2006). Other studies (Johnson et al. 2000, Johnson et al. 2003, Johnson et al. 2007) that have been conducted in individuals actively drinking can be considered

abstinence initiation trials (Swift 2003), where the primary measure of efficacy was a reduction in alcohol consumption from baseline. A medication with demonstrated efficacy in actively drinking alcohol-dependent outpatients would have greater clinical applicability than a medication that is only efficacious in individuals who have already achieved abstinence. Since pregabalin can be titrated quickly to clinically relevant doses (300 mg/day in one week), an immediate or early effect of pharmacotherapy should be neuroinhibition.

The development of safe and effective pharmacotherapies for alcohol dependence remains an important public health need. A significant gap in the AUD pharmacotherapy armamentarium exists; no agent has been identified that can be safely administered to actively drinking outpatients to treat withdrawal, promote abstinence, and reduce the risk of relapse. No current pharmacotherapy for alcohol dependence meets these criteria. The proposed project builds on our promising pilot data (see preliminary studies) testing gabapentin as an abstinence initiation strategy for alcohol dependence. The proposed trial aims to study the ideal dosing, tolerability, and safety of pregabalin when administered to actively drinking patients with AUD. This would be the first abstinence initiation trial using pregabalin.

## Specific Aims and Hypotheses

### Specific Aims and Hypotheses

#### Primary Outcome Measures

- 1) **Maximum dose pregabalin:** Defined as the highest amount of medication per day maintained for a 7 day period.
- 2) **Pregabalin Tolerability:** Adverse effects, as measured by the Systematic Assessment for Treatment and Emergent Events (SAFTEE), will calculated by both a symptom count per week and over the course of the study period. The relationship of adverse effects on compliance and outcome will be assessed.

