#### **Hypotheses testing:**

- 1) **Primary Hypothesis:** The mean maximum tolerated dose and mean adverse symptoms count will be calculated.
- 2) **Secondary Hypotheses:** Paired-samples T tests will be used to compare baseline assessments to end-of-study assessments for continuous variables (e.g., craving or withdrawal scores) and the chi-square test will

---

be used for variables reported as proportions (e.g., percent days abstinent, proportion heavy drinking days).

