## **Description of Subject Population**

### **Sample #1**

Specify subject population

Adults with AUD

Number of completers required to accomplish study aims

10

Projected number of subjects who will be enrolled to obtain required number of completers

20

Age range of subject population

18-65

Gender, Racial and Ethnic Breakdown

We plan to enroll 20 participants into the study. Both males and females will be recruited. All eligible participants are accepted; however, past experience with recruitment at STARS suggests that the approximate gender distribution for this study will likely be 20% female and 80% male. Previous and ongoing studies at STARS have had samples comprised of approximately 50% Caucasians, and 50% ethnic minorities distributed as 24% African-American and 22% Hispanic-American, and 4% other. We anticipate a similar representation in this project. We will make every effort to recruit minority patients in order to ensure the generalizability of our findings to the overall treatment population.

Description of subject population

We plan to enroll 20 participants into the study who meet criteria for current AUD.

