## Study Procedures

Describe the procedures required for this study

*Study Participants:* Participants will be 20 men and nonpregnant women with AUD who report drinking a minimum of 5 standard drinks for men or 4 standard drinks for women at least 4 days per week over the past 28 days. The daily minimum drinking requirements are consistent with the commonly accepted definition of “binge drinking.” A minimum requirement of having a heavy drinking episode 4 days a week would select for a population of individuals who are drinking excessively more days than not. An exclusion threshold CIWA-Ar score of  $\geq 13$  is set to balance the need to protect participants from the consequences of untreated severe alcohol withdrawal symptoms and the need for the enrolled patients to have alcohol withdrawal symptoms of sufficient severity to detect between group differences. During the first two weeks of the study participants will be monitored frequently for the development of severe alcohol withdrawal symptoms. The gabapentin pilot study used an exclusion cut-off of CIWA-Ar score of  $\geq 13$  and there were no serious adverse events and no participants were removed from the trial due to the development of alcohol withdrawal, suggesting that a CIWA-Ar eligibility and drop-out threshold  $\geq 13$  combined with careful monitoring will appropriately protect participants from the risk of untreated alcohol withdrawal symptoms.

**Design Overview:** In a 9-week open label outpatient pilot trial, the ideal dosing, tolerability, and safety of pregabalin will be tested in 20 outpatients with AUD. The specific aims of the project are to determine in AUD outpatients 1) Pregabalin will be well tolerated and safe when used as an abstinence-initiation agent in AUD outpatients in doses ranging up to 600 mg per day. 2) the ideal target dose range and tolerability of pregabalin pharmacotherapy. Secondary outcome measures will be the end-of-study proportion of heavy drinking days and percent days abstinent compared to baseline. Exploratory measures include: 1) alcohol use as measured by secondary outcomes such as amount of drinks per day; and 2) the symptoms of alcohol withdrawal.

**Medication:** Pregabalin will be prepared by our pharmacy at the NY SPI. Pregabalin will be administered in 75 mg and 100 capsules. Pregabalin will be titrated over a 3-week period to the FDA maximum (600 mg per

---

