**Assessment of Side Effects and Medication Compliance:** The research nurse and psychiatrist will query about side effects related to the study medication. Reported side effects and other treatment emergent events since the past visit will be recorded; additionally, the severity of the side effect/treatment emergent event, the action taken, and the continuation or resolution of the side effect/treatment emergent event will be documented.

**Medication Adherence Enhancement:** We will use a timeline followback interview and pill count with a weekly financial incentive (\$10) for medication bottle return to both enhance and measure medication adherence. Our prior studies have found a 91% rate of bottle return using this method. Participants are not provided reinforcement for ingesting medication—payment is tied solely to the return of the medication bottle. We considered serum blood levels and riboflavin over-encapsulation and fluorometric quantification, but decided those interventions were not cost-effective given the limited budget of this open-label investigation.

**Medical Management Treatment:** All participants will have a weekly supportive behavioral treatment session with the research psychiatrist using a manual designed for pharmacotherapy trials in subjects with alcohol use disorders (Pettinati et al. 2005). This psychosocial intervention facilitates compliance with study medication and other study procedures, promotes abstinence from marijuana and other substances,

---

and encourages mutual-support group attendance. [name] will provide ongoing supervision to other study physicians to prevent therapeutic drift. All study psychiatrists will be trained in providing Medical Management and refresher training sessions will be provided every 6 months. As director of Columbia's Substance Treatment and Research Service, [name] has extensive experience conducting and supervising Medical Management and other similar medication adherence focused psychosocial intervention models.

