**Study Visits:** Study visits will occur daily for the first 4 days of the study period. During the second week, patients will be asked to attend 3 study visits. During the remainder of the 8-week study period, study visits will occur twice weekly. There will be one visit during the taper week (week 9). There will be final post-taper visit after study medication is discontinued (week 10). One visit per week will be with the research psychiatrist. Participants will receive \$10 per visit for transportation expenses.

You can upload charts or diagrams if any  
table 1.medication dosing schedule.pdf

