### Interviews

1. **Alcohol Timeline Follow-Back (TLFB-A):** The alcohol timeline Followback method (Litten and Allen 1992) will gather self-reported alcohol use data.
2. **Clinical Global Impression Scale-Observer (CGI):** The CGI-Severity and -Improvement scales (Guy 1976) will be used to measure the overall clinical status of the subject and change from baseline.
3. **Clinical Institute Withdrawal Assessment-Alcohol (CIWA-Ar):** The CIWA-Ar (Sullivan et al. 1989), a 10-item scale, is the most widely-used measure of alcohol withdrawal symptoms.
4. **Hamilton Anxiety Scale (HAMA):** The HAM-A (Hamilton 1959) is a 14-item instrument widely used to measure current anxiety symptoms.
5. **SAFTEE:** The Systematic Assessment for Treatment and Emergent Events (SAFTEE) modified for the COMBINE study (Johnson et al. 2005) will be performed at each study visit.
6. **Psychiatric Evaluation and Diagnosis:** The MINI International Neuropsychiatric Interview will be performed during screening as part of a complete psychiatric diagnostic assessment.
7. **Structured Pill Count Interview:** The Structured Pill Count Interview is a Timeline Follow-Back assessment of study medication compliance accounting for each dose of prescribed study medication.
8. **Modified Treatment Services Review (TSR):** The Modified Treatment Services Review is an 18-item questionnaire modified from the Treatment Services Review (McLellan et al. 1992) that assesses the past week exposure of the subject to health care and substance use disorder treatment.

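### The SAP leaves out the protocol's second primary outcome, the SAFTEE symptom count, and its promised relation to compliance and outcome; when restored, the count should be reported with time observed

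*Protocol*

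**What the plan says.** The protocol lists two primary outcome measures under Specific Aims and Hypotheses. The first is the maximum dose of pregabalin maintained for a week. The second is tolerability: adverse effects measured by the SAFTEE "will calculated by both a symptom count per week and over the course of the study period". The same item adds: "The relationship of adverse effects on compliance and outcome will be assessed". Under Hypotheses testing, the analysis for the primary hypothesis is: "The mean maximum tolerated dose and mean adverse symptoms count will be calculated". No method is given for the relation.

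Under Assessment Instruments (Interviews), the SAFTEE "will be performed at each study visit". Under Description of Subject Population, 10 completers are required, and the entry for "Projected number of subjects who will be enrolled to obtain required number of completers" is 20.

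The SAP (Statistical Analyses) refers to the primary outcome measure in the singular and gives only maximum maintained dose, with mean and standard deviation. Side effects become three indicators per participant: any side effect, any dose reduction because of side effects, and any stopping of medication because of side effects. Retention is summarised separately, as proportions and mean weeks completed. The SAP does not mention the SAFTEE, a symptom count (weekly or whole-study), compliance, or any analysis relating adverse effects to compliance or outcome.

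**The concern.** Tolerability is half of the stated primary objective (Lay Summary). A count and an any-side-effect indicator answer different questions: the indicator scores one brief mild complaint the same as many persistent ones. In a sample of 20 on an active drug, most participants may score yes, and the indicator would then say little about burden. If the analysis follows the SAP, readers will not see the measure that the protocol named in advance, and the SAP gives no reason for the change.

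A second matter arises once the count is restored. A whole-study total grows with time observed. Someone who leaves early has fewer SAFTEE assessments, so a mean total shown without time observed can make tolerability look better than it was. A raw total would also carry time on study into the promised comparison with compliance and outcome.

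**Working it through.** **1. Protocol against SAP**

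- SAFTEE count per week: primary in the protocol; absent from the SAP.
- SAFTEE count over the study: primary in the protocol, with a mean planned; absent from the SAP.
- Relation of adverse effects to compliance and outcome: promised in the protocol; absent from the SAP.
- Maximum dose: primary in both.
- Side-effect indicators and retention: in the SAP, not labelled primary.

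The omission is read directly from the text and rests on no assumption.

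**2. Number of SAFTEE assessments.** Study Procedures states: "Study visits will occur daily for the first 4 days of the study period". Week 2 has 3 visits, and weeks 3 to 8 have 2 each. So 4 + 3 + 6 × 2 = 19, which matches the 19 visits under Compensation. The payments also agree: (19 + 1 + 1) × $10 = $210 for travel, plus 9 × $10 = $90 for bottles, total $300. Through week 2 there are 4 + 3 = 7 visits, and 7/19 = 36.8%.

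**3. Direction.** Let c_k ≥ 0 be a participant's count in week k, and T(w) = c_1 + … + c_w. Then T(w) ≤ T(9) for any leaving week w. Leaving early lowers the cumulative total or leaves it unchanged. The same holds for the mean over all treated participants. It need not hold for a completers-only mean, which could move either way.

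**4. Size, illustration only.** Assume the same constant weekly count for everyone, 9 weeks, 20 participants all analysed, and L leaving after week w. The mean total as a share of its full-follow-up value is [(20 − L) × 9 + L × w] / (20 × 9).

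- L = 10: w = 2, 110/180 = 61%; w = 4, 130/180 = 72%; w = 6, 150/180 = 83%.
- L = 5: 145/180 = 81%; 155/180 = 86%; 165/180 = 92%.
- L = 2: 166/180 = 92%; 170/180 = 94%; 174/180 = 97%.

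Dividing each total by weeks observed gives 100% throughout, but only because the weekly count was assumed constant. If the total counts distinct symptoms and all have appeared before anyone leaves, it does not fall at all.

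**5. Where the rate misleads.** The protocol states: "Pregabalin will be titrated over a 3-week period". Suppose 4 symptoms per week in weeks 1 to 3 and 1 per week in weeks 4 to 9. A full-term participant totals 3 × 4 + 6 × 1 = 18, a rate of 18/9 = 2.0. The same person leaving after week 2 totals 8, a rate of 8/2 = 4.0. The total is too low and the rate too high, so neither should stand alone.

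**6. Relation analysis.** At 2 symptoms per week, leaving after week 2 gives a total of 4 and staying 9 weeks gives 18. The raw totals differ only through time on study; the rates are equal.

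**The case against.** The strongest reply is that the understatement in a whole-study total arises under neither document as written. The SAP plans no total, so it cannot mislead. The protocol plans weekly and whole-study counts together, so the total never stands alone. This is correct. The exposure point is a condition on how the count is restored and not a bias already in the plan.

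It can also be said that the SAP is brief, does not claim to replace the protocol, and still describes tolerability through dose reductions, discontinuation, retention and maximum dose. A reader might infer that tolerability has been dropped. It has not, and those summaries are useful. What is missing is the count and the relation analysis, and nothing in the SAP supplies either.

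Two further inferences go too far. One is that reported burden will be understated by a large, known percentage because those with more symptoms leave. The documents give no symptom rates, leaving times or reasons for leaving. The 10 of 20 allows for non-completion of any kind, and side effects are not among the listed early-discontinuation criteria. The other is that the plan has no rule for a symptom reported at several visits. None is visible, but the attached assessment schedule or the cited SAFTEE instrument may contain one. The protocol also records whether each event continues or resolves ("Reported side effects and other treatment emergent events since the past visit will be recorded", with severity, action and outcome), so the data could support several rules.

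**Conclusion.** The protocol–SAP mismatch stands without qualification: a declared primary outcome and a promised analysis have no place in the SAP. It should be corrected. The outcome is descriptive, so no test, significance level or power figure is affected.

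The exposure point stands for each participant's cumulative total and for the mean over all treated participants. Its size is unknown. The 61% to 97% range in the working rests on a constant, equal weekly count and chosen leaving patterns, and the shortfall could be nil under a distinct-symptom count. It supports showing time observed beside the total. It does not support a claim that the trial's tolerability result will be biased by any stated amount.

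**What to change.** In the SAP:

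- Name the SAFTEE symptom count as a primary outcome beside maximum maintained dose, and state or cite the counting rule and whether weeks 9 and 10 are included.
- Report the weekly mean count with the number of participants contributing each week, since later means come only from those still attending.
- Report the whole-study total over all treated participants, together with weeks observed and the count per observed week. State how many have no assessed week.
- Add a descriptive summary of the relation between the per-week rate and both pill-count compliance and a named drinking outcome already in the SAP. The choice of summary is open. With 20 participants it will be imprecise: an observed rank correlation of 0.3 has an approximate 95% interval of −0.17 to 0.66, from tanh(atanh(0.3) ± 1.96 × √((1 + 0.3²/2)/17)).
- Keep the dose-reduction, discontinuation and retention summaries.

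The cost is SAP wording and a little programming. SAFTEE and pill-count data are already collected. The drawback is that rates for early leavers rest on few weeks within titration and may be high, so they must be read with the weekly means and the total.

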#### Secondary Outcome Measures

- 1) **The proportion of the heavy drinking days** (defined as any day where the number of standard drinks was at least 5 for men and at least 4 for women) per week
- 2) **The percent days abstinent** will be lower at the end of the trial as compared to baseline.
- 3) **Symptoms of alcohol withdrawal** will be reduced as compared to baseline.

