### Physiological Measures

1. **Alcohol Breath Testing:** Alcohol breath testing will be performed at every study visit.
2. **Medical History and Physical Exam:** A comprehensive medical history and physical examination will be performed on all participants during the screening process.
3. **Pregnancy Testing:** Serum pregnancy testing will be performed during screening and a urine pregnancy test will be performed at study weeks 4 and 8.
4. **Serum laboratory examination:** Complete blood count, electrolytes, and liver function tests will be performed during the screening process.
5. **Urinalysis:** Laboratory urinalysis (glucose, protein, ketones, pH, specific gravity, microscopic analysis) will be performed during the screening process.
6. **Urine Toxicology:** Urine samples for toxicology will be collected under directly observed conditions during screening and study weeks 4 and 8 to detect any non-alcohol substance use.
7. **Vital Signs:** Temperature, pulse, and blood pressure will be measured at every study visit for data collection and safety monitoring purposes.

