#### Describe procedures for minimizing risks

Participants are carefully screened for psychiatric risk prior to admission, so we anticipate the risk of clinically-significant psychological deterioration during participation to be low. The exclusion criteria are designed to minimize the medical and psychiatric risks to participants as discussed above, including risks of adverse events and side effects. All patients will be informed of the possible side effects and risks through extensive discussions with the research psychiatrist during the consent process.

Alcohol withdrawal will be assessed at each study visit using the Clinical Institute Withdrawal Alcohol (CIWA-AR). Anxiety and drinking will be assessed weekly.

Participants will provide a blood sample during screening; they will be warned that blood drawing may cause slight discomfort at the site of needle entry and may result in a small bruise.

Patients are informed prior to study entry that they can refuse to answer any questions and that they can request to stop at any time. If a participant becomes agitated during any of the interviews or assessments, he or she will be provided with therapeutic assistance.

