Study: AN OPEN-LABEL PILOT STUDY OF PREGABALIN AS TREATMENT FOR ALCOHOL USE DISORDERS

PI: [name]

IRB: 7491

NCT#: NCT03256253

Data Analysis Plan created 6-28-2017

Statistical Analyses

Summary statistics of baseline demographics of the sample will be computed using frequencies, means and standard deviations. For skewed distributions, medians and interquartile ranges (IQR) will be computed. Study retention will be summarized using proportions and by computing the mean number of weeks in the trial completed.

For the primary outcome measure, the maximum maintained dose will be reported with mean and standard deviation. For measures of drinking and abstinence for each participant it will be computed during the participant's last week of study participation: proportion of heavy drinking days, proportion of abstinent days, number of drinks per week, and number of drinks per drinking day. The same measures will be computed at baseline using the weekly average over the past 28 days. Wilcoxon signed rank tests will be used to analyze the change from baseline to the last week of study participation. Side effects will be summarized by creating indicators of whether subjects reported: any side effects during the trial, any dose reductions due to side effects, and any discontinuation of medication due to side effects. All analyses will be conducted in SAS® (version 9.4) and all statistical tests were 2-tailed at a significance level of 5%.

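### The planned change in CIWA-Ar mixes any drug effect with a change in how recently participants drank, and the SAP omits the outcome altogether

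*Protocol*

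**What the plan says.** **Outcome.** Protocol, Secondary Outcome Measures, item 3, states that withdrawal symptoms "will be reduced as compared to baseline". The Design Overview under Study Procedures lists the same symptoms as exploratory.

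**Instrument and timing.** Protocol, Interviews, says the CIWA-Ar "is the most widely-used measure of alcohol withdrawal symptoms". The section on minimizing risks says "Alcohol withdrawal will be assessed at each study visit". Neither section sets a condition on time since the last drink.

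**Test.** Protocol, Hypotheses testing: "Paired-samples T tests will be used to compare baseline assessments to end-of-study assessments for continuous variables (e.g., craving or withdrawal scores"). There is no covariate, stratum or condition on drinking.

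**Rationale.** Protocol, Background, describes insomnia, anxiety and craving as features of the withdrawal and post-withdrawal state, and continues: "Emergence of these symptoms, which can be relieved by alcohol consumption". It then says that cutting down or stopping produces neuroexcitation in a dependent person.

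**Drinking data.** Protocol, Physiological Measures: "Alcohol breath testing will be performed at every study visit". The Timeline Follow-Back (TLFB) is listed under Interviews. No section links either of them to the CIWA-Ar.

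**SAP.** The change analyses cover "proportion of heavy drinking days, proportion of abstinent days, number of drinks per week, and number of drinks per drinking day". The stated method is "Wilcoxon signed rank tests will be used to analyze the change from baseline to the last week of study participation". Withdrawal and the CIWA-Ar are not mentioned.

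**The concern.** The trial enrols people who are actively drinking and hopes they will stop. On the protocol's own account, drinking relieves withdrawal-related symptoms and stopping brings them on. A CIWA-Ar score therefore reflects partly the participant's state on the day and partly anything the drug does.

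The intended effect of treatment, abstinence, changes the condition under which this outcome is measured, and there is no control arm in which the same change would show. A low score at the end of study has at least three readings: protection by the drug, a recent drink, or withdrawal that resolved weeks before. The paired test cannot tell them apart.

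What is at stake is one stated motive for the trial, a drug that protects against withdrawal while people stop drinking. The primary outcomes, maximum dose and tolerability, are not affected.

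**Working it through.** **No stated figure to reproduce.** The documents give no expected CIWA-Ar change, standard deviation or power for this outcome. The calculation below shows direction and scale only.

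**Inputs from the documents.** Enrolment 20 and completers required 10 (Description of Subject Population); single-arm open-label design (Design Overview); paired t test (Hypotheses testing); two-sided 5% level (SAP).

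**Assumed inputs, not in the documents.** Mean CIWA-Ar 6 unless newly abstinent, and S points higher when newly abstinent, with S = 0, 2 or 4. People long past withdrawal are taken to score like drinkers. SD is 3 around the state mean at each assessment, baseline and end-of-study scores are independent, and the true drug effect is zero.

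**Step 1: mean change.** Let p0 and p1 be the shares newly abstinent at baseline and at end of study.

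Mean change = S × (p1 − p0)

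- Share falls from 50% to 10%: 2 × (−0.4) = −0.8; 4 × (−0.4) = −1.6.
- Share rises from 10% to 50%: 2 × 0.4 = +0.8; 4 × 0.4 = +1.6.
- Share unchanged, or S = 0: 0.

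**Step 2: size relative to the SD of the change.**

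Variance of change = 9 + 9 + S² × [p0(1 − p0) + p1(1 − p1)], where the bracket is 0.25 + 0.09 = 0.34.

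- S = 2: 18 + 4 × 0.34 = 19.36, SD 4.40; 0.8 / 4.40 = 0.18.
- S = 4: 18 + 16 × 0.34 = 23.44, SD 4.84; 1.6 / 4.84 = 0.33.

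For comparison, the paired t test has 80% power only for a standardised change of about 1.00 with 10 pairs or 0.66 with 20. The artefact is smaller than what this trial could reliably detect.

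**Step 3: false-positive rate.** The planned test was simulated 20,000 times per scenario. The nominal rate in each direction is 2.5%.

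| Share newly abstinent | Pairs | False result | S = 2 | S = 4 |
|---|---|---|---|---|
| 50% to 10% | 10 | reduction | 7.5% | 15.7% |
| 50% to 10% | 20 | reduction | 11.6% | 29.2% |
| 10% to 50% | 10 | worsening | 7.6% | 15.6% |
| 10% to 50% | 20 | worsening | 11.8% | 28.6% |

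With S = 0 or an unchanged mix, the simulated rates stay close to 2.5%.

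**Step 4: is the missing link supplied elsewhere?** The protocol analyses withdrawal without drinking status, and the SAP does not analyse withdrawal. Breath alcohol and TLFB appear only as assessments. The gap is open in both documents.

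**The case against.** **Direction.** A reader might infer that participants who keep drinking will look protected. The documents do not support that. The test is on change from baseline, so someone who has drunk recently at both assessments shows no change, which is a null result. If everyone is drinking at baseline, the artefact can only run against the drug. With assumed scores of 3 after recent drinking and 8 when newly abstinent, and 6 of 20 newly abstinent at the end, the mean goes from 3.0 to (14 × 3 + 6 × 8)/20 = 4.5. A false reduction needs fewer newly abstinent people at the end than at baseline. The documents fix neither share. This objection stands, and it is why no net sign is claimed here.

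**Timing.** A reader might also infer that scores from all visits are pooled. They are not: the protocol compares baseline with a single end-of-study assessment. By then, someone who stopped early may be well past withdrawal. That reduces the number likely to be newly abstinent at the end, but it adds the third reading of a low score, so the result remains ambiguous.

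**The rationale does not name the CIWA-Ar.** Correct. The symptoms that Background lists are insomnia, anxiety and craving, which have their own scales in the protocol. The link to the CIWA-Ar is an inference, through its description as the withdrawal measure and through the sentence on neuroexcitation.

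**Small uncontrolled pilot.** Without a control arm, no handling of drinking status would let this comparison establish protection. That also stands. It argues for a descriptive label and a modest remedy, not for leaving the test as it is.

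**Conclusion.** The concern holds in a limited form. The planned CIWA-Ar comparison is unconditioned, the protocol's own rationale makes a score depend partly on recent drinking, and no control arm absorbs the difference. The mean change can therefore move in either direction with no drug effect.

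The sign and size cannot be derived from the documents. Under the assumed values, a 40-point shift in the newly abstinent share moves the mean by 0.8 to 1.6 points and lifts the false-positive rate in that direction from 2.5% to between 7.5% and 29.2%. If the score does not depend on drinking status, or the mix is the same at both assessments, there is no bias.

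This restricts what may be concluded about withdrawal. It does not touch dose or tolerability. The SAP's silence on withdrawal comes first, since the outcome has to be brought into the plan before its handling can be settled.

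**What to change.** 1. Add withdrawal (CIWA-Ar) to the SAP and keep the baseline to end-of-study comparison.
2. Beside it, tabulate CIWA-Ar at baseline and at each visit by same-visit breath alcohol (zero or positive) and by days since last drink from the TLFB.
3. Label the result descriptive. State that a fall will not be read as protection against withdrawal unless it also appears in scores taken at zero breath alcohol in the first days after the last drink.
4. Do not replace the main comparison with a zero-breath-alcohol subset. Drinking after baseline is itself an outcome, so that would select on response, and with 10 completers required it could leave very few pairs.
5. Confirm that breath alcohol is measured when the baseline CIWA-Ar is taken. Physiological Measures commits to it only at study visits.
6. Reconcile Secondary Outcome Measures (secondary) with the Design Overview (exploratory).

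**Cost.** SAP text and a data merge. No new data collection is needed if step 5 is confirmed. The table will have small cells, and the claim for this outcome becomes weaker.
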